8. SAFETY ANALYSIS

The as-treated population will be used for all of the safety analyses. All safety data will be listed.

8.1 Changes to the Planned Safety Analysis Proposed in Protocol

None.

8.2 Adverse Events and Other Complications

As part of this registry, only infections, clinically meaningful laboratory abnormalities (except infections) and Revcovi related adverse events will be recorded in the eCRF. A treatment-emergent AE will be defined as an AE with an onset date at or after the reported start date of Revcovi in the CLI-06814AA1-01 study and no later than 30 days after the last dose of Revcovi. All adverse events will be coded using the Medical Dictionary for Regulatory Activities (MedDRA) Version 22.1 or the most recent version prior to database lock. Summaries will be presented for all treatment-emergent adverse events (overall and by severity), adverse events determined by the investigator to be treatment-related (overall and by severity), serious adverse events (SAEs), adverse events causing discontinuation from Revcovi, and non-serious AEs. In addition to being summarized as adverse events, infectious complications and hospitalizations are considered efficacy measures as summarized in Section 7.2.3.

The frequency of adverse events will be summarized using descriptive statistics by system organ class (SOC), preferred term and subject status. Subjects are counted only once in each SOC category, and only once in each preferred term category. Treatment-related adverse event summaries will include adverse events with missing relationship to study drug. For the summaries by severity, subjects with multiple events are counted only once at the greatest non-missing severity. If all are of missing severity grade, then the AE term (SOC or PT) will be included in "Missing" severity category. Adverse events missing the flag indicating serious will be excluded from the summary of serious adverse events but included in the summary of non-serious adverse events. The total number of adverse events and serious adverse events and the corresponding yearly rates will also be reported.

Listings for all adverse events, deaths, serious adverse events and adverse events leading to study drug discontinuation will be presented. AEs from STP-2279-002 subjects with an onset date prior to the first documented dose of Revcovi in the CLI-06814AA1-01 study and a resolution date after the reported start date of Revcovi in the CLI-06814AA1-01 study or an outcome of ongoing, will be included in the AE listings but not in the summary tables.

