13.2.3.5 Safety Data Analysis

Safety summaries will be presented by whether or not they previously participated in study STP-2279-002.

Adverse Events and Serious Adverse Events – AEs will be categorized using Medical Dictionary for Regulatory Activities (MedDRA) Version 22.1 or later. Summaries will be presented for all treatment-emergent AEs, AEs determined by the Investigator to be treatment-related, serious adverse events (SAEs), AEs causing withdrawal from study, AEs causing discontinuation of Revcovi, and non-serious AEs. The intensity of toxicities will be graded by the Investigator as mild, moderate, or severe as described in Section 12.2.5. In addition to being summarized as AEs, infectious complications and hospitalizations are considered efficacy measures as described in Section 10.8.

AE incidence will be calculated based on the number of subjects per AE category. For each subject who has multiple AEs classified to the same category, that subject will be tabulated under the maximum toxicity intensity for that AE category. The incidence of AEs will be tabulated by MedDRA system organ class and preferred term.

An AE onset between the date of the first dose of Revcovi and 30 days after the last dose of Revcovi is considered as a treatment-emergent AE.

Laboratory Safety Data – Hematology, chemistry, and urinalysis data will be summarized by timepoint of collection and by treatment group. In addition, listings for laboratory data will be presented identifying clinically significant abnormal results and out-of-normal range values will be listed.

Other Safety Data – The results of antibodies against Revcovi and antibodies against PEG will be summarized. The relationships between immunogenicity, biochemical endpoints, and the clinical toxicities will be examined as appropriate. Concomitant medications and findings in physical examinations will be listed and described textually as recorded in the CRF. Descriptive statistics of vital signs measurements as well as changes from baseline will be tabulated; abnormal vital sign values will be reported and summarized as AEs.

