2. STUDY OBJECTIVES

2.1 **Objectives**

To conduct a registry study on patients, with adenosine deaminase severe combined immune deficiency (ADA-SCID) treated with Revcovi[®] and have periodic clinical and biochemical assessments for safety and dose adjustment based on adenosine deaminase (ADA) activity and erythrocyte deoxyadenosine nucleotide (dAXP) levels and/or clinical assessment by the treating physician. The study will include Adagen-naïve patients started on de novo enzyme replacement therapy (ERT) with Revcovi or converted from Adagen to Revcovi, over the course of 2 years and continued to be followed until the last enrolled patient has 2 years of follow up. Patients who are expected to receive 3 to 4 months of ERT prior to proceeding to hematopoietic stem cell transplantation (HSCT) or gene therapy will also be included in the study.

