5. GENERAL ANALYSIS CONSIDERATIONS

All analysis will be descriptive and no statistical hypothesis will be tested. Descriptive statistics for continuous variables will include number of observations (n), mean, standard deviation (SD), median, minimum (min), and maximum (max); for categorial variables counts and percentages for each category. Ninety-five percent confidence intervals (CIs) will be calculated for the main outcome variables without adjustment for multiplicity to generalize the results to the general population. If not otherwise noted, confidence intervals for continuous variables will be based on normal distribution, for categorial variables on Clopper-Pearson (Clopper and Pearson 1934). Confidence intervals for Poisson distributions will be calculated by the method of Ulm (Ulm 1990).

Time to event analyses will be performed by the Kaplan-Meier method (Kaplan and Meier 1958). Confidence intervals for the median survival time will be calculated based on the method of Brookmeyer and Crowley (Brookmeyer and Crowley 1982) after log-log transformation.

All analyses will be performed by subject status (Adagen-Naïve subject, Adagen-Transitioning subject, or STP-2279-002 participant) and overall. Subject status is as collected on the Adagen/Revcovi Treatment page in the eCRF. There is a different recommended visit schema for the Adagen naïve subjects and the Adagen transitioning subjects (Table 1 and Table 2). However, a data review revealed that the timing of the assessments is not following the suggested visit schema. Therefore, the slotting schema within each subject status will be uniform for all assessments. All assessments will be slotted to the closest visit suggested for the Adagen transitioning or Adagen naïve subjects, respectively, regardless of whether or not the specific assessment is recommended for this visit, Participants of the STP 2279-002 study will be analyzed per the Suggested Schedule of Assessments for Adagen-Transitioning Subjects. Therefore, the visit windows will be specific for each type of subjects (see Section 13.3). All visits will be included in the overall column, regardless of whether or not the specific visit is analyzed for all type of subjects.

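### SAP 8.2 gives treatment-related AEs and the SOC/PT tables no exposure-adjusted measure, although follow-up is unequal by design, so differences in percentages can reflect exposure time alone

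*SAP*

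**What the plan says.** SAP section 8.2 lists summaries of all treatment-emergent AEs, treatment-related AEs, SAEs, AEs causing discontinuation of Revcovi and non-serious AEs. The measure is set out as follows.

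- "The frequency of adverse events will be summarized using descriptive statistics by system organ class (SOC), preferred term and subject status" (SAP 8.2).
- "Subjects are counted only once in each SOC category, and only once in each preferred term category" (SAP 8.2).
- Descriptive statistics mean, "for categorial variables counts and percentages for each category" (SAP 5).
- "All analyses will be performed by subject status (Adagen-Naïve subject, Adagen-Transitioning subject, or STP-2279-002 participant) and overall" (SAP 5).
- The protocol uses the same unit: "AE incidence will be calculated based on the number of subjects per AE category" (Protocol 13.2.3.5).

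The only exposure adjustment in 8.2 is one sentence: "The total number of adverse events and serious adverse events and the corresponding yearly rates will also be reported". It names no rate for treatment-related AEs or for any SOC or PT, and it does not define the person-time behind the rates. Section 8.2 also says which events reach the eCRF: infections, clinically meaningful laboratory abnormalities and Revcovi-related AEs.

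On follow-up, SAP 2.1 includes "Patients who are expected to receive 3 to 4 months of ERT prior to proceeding to hematopoietic stem cell transplantation (HSCT) or gene therapy". Protocol 7.1 follows other subjects until the last enrolled patient has at least 24 months of treatment. Enrolment is open for at least 2 years (Protocol 13.1), and Protocol Appendices 1 and 2 schedule visits to Treatment Month 48. A treatment-emergent AE starts on or after the reported Revcovi start date in this registry and no later than 30 days after the last dose (SAP 8.2 and 13.5).

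**The concern.** A percentage of subjects with at least one event rises with time at risk. Placed in columns whose subjects were observed for very different times, it mixes the rate of harm with the length of observation. That is the situation in the tables meant to characterise reactions to Revcovi.

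A stated purpose of the registry is to collect safety data in patients started de novo on Revcovi (Protocol 6.1). If the status groups differ in follow-up, two groups with the same rate will show different percentages, and a group with a higher rate but short follow-up can show the lower one. The overall column has the same weakness: it depends on the mix of short and long courses.

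The total AE rate cannot fill the gap, because its numerator includes infections and laboratory abnormalities whether or not they are attributed to the drug.

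**Working it through.** The documents give no sample size, AE rate or exposure by status group, so there is no figure of the plan's own to reproduce. The check asks how far the planned percentage moves when only exposure changes.

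**Inputs from the documents**
- Short course: 3 to 4 months of treatment (SAP 2.1). With the 30-day tail, 4 months is (4 × 30.4375 + 30)/365.25 = 0.415 years; 3 months is 0.332 years.
- Longer courses: 2 years (the minimum follow-up target) and 4 years (the last scheduled visit in the protocol appendices). With the tail, 2.082 and 4.082 years.

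**Assumptions**
- The same constant rate λ of first events per patient-year in every group. The documents give no rate, so λ = 0.05 to 0.50 is illustrative.
- Every subject in a group is followed for the full time shown.

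**Formula.** Expected percentage affected = 100 × (1 − exp(−λT)).

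At λ = 0.10:
- T = 0.415: 1 − exp(−0.0415) = 4.1%
- T = 2.082: 1 − exp(−0.2082) = 18.8%
- T = 4.082: 1 − exp(−0.4082) = 33.5%

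Over the range of λ:

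| λ per patient-year | 4 months | 2 years | 4 years | Ratio 2 y / 4 mo | Ratio 4 y / 4 mo |
|---|---|---|---|---|---|
| 0.05 | 2.1% | 9.9% | 18.5% | 4.8 | 9.0 |
| 0.10 | 4.1% | 18.8% | 33.5% | 4.6 | 8.2 |
| 0.25 | 9.9% | 40.6% | 64.0% | 4.1 | 6.5 |
| 0.50 | 18.8% | 64.7% | 87.0% | 3.4 | 4.6 |

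All rows include the 30-day tail. Within each row the true rate is the same in all three groups.

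**The order can reverse.** A group with twice the rate (0.20) and a 4-month course shows 1 − exp(−0.20 × 0.415) = 8.0%. A group with rate 0.10 and 4 years shows 33.5%. For equal percentages the 4-month group would need 4.082/0.415 = 9.8 times the rate.

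**The overall column.** At λ = 0.10, a column with half its subjects at 4 months and half at 4 years shows (4.1 + 33.5)/2 = 18.8%. With a quarter at 4 months it shows 0.25 × 4.1 + 0.75 × 33.5 = 26.2%. The mix is assumed; the rate has not changed.

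**After the fix.** Under the same assumption, events divided by patient-years at risk have the same expected value of 0.10 in each group, whatever T is.

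**The case against.** **The plan is descriptive.** There is no hypothesis test, and 8.2 does not say that status groups will be compared. That is true, and the percentages are not wrong as counts. But columns side by side invite comparison, and the overall column is affected without any.

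**Exposure is already reported.** Total AE and SAE rates are planned and, under SAP 5, fall by status. SAP 8.7 summarises treatment duration by status. This helps a careful reader, but neither gives a rate for treatment-related events.

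**Infections are already handled.** SAP 7.2.3 tabulates documented infections by SOC and PT within yearly periods and gives an incidence rate with confidence intervals by the method of Ulm; hospitalizations are treated similarly. So one could not say that every SOC/PT result in the plan is a crude percentage over unequal follow-up. The cover is partial: anyone with one day in a period enters the denominator, and the rate is for all infections together. Non-infectious treatment-related AEs get nothing comparable.

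**Follow-up of about nine years.** A reader might infer this from the period and visit grids, which end at day 3286 (3286/365.25 = 9.0 years). The documents do not support that as AE time at risk. For STP-2279-002 subjects the grid counts from the first dose in the earlier study (SAP 13.2 and 13.3), while treatment-emergent AEs count only from the registry start date. From the stated October 2017 approval to the SAP date of 06 June 2023 is 5.6 to 5.7 years, which bounds commercial exposure at that date if none preceded approval. The point needs only 4 months against 2 years.

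**Adagen-naïve subjects will look safer.** A reader might infer this too. It would follow if the bridging subjects were mostly naïve, but preparing for transplant or gene therapy is a separate entry criterion (Protocol 9.2), and no section ties it to naïve status.

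**Rates have their own weaknesses.** One subject with recurrent events can dominate an event rate in a small group. If events cluster early, a rate understates early risk in the long-exposure groups. PT-level rates will be sparse. All of this stands, and it argues for showing rates beside counts and for not requiring a rate in every PT cell.

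**Conclusion.** The point holds in limited form. In SAP 8.2, treatment-related AEs and the SOC/PT tables have no exposure-adjusted measure, while follow-up is planned to range from 3 to 4 months up to 2 to 4 years. With the true rate held equal, exposure alone can multiply the percentage affected by about 3.4 to 4.8 (2 years against 4 months) or 4.6 to 9.0 (4 years against 4 months) for rates of 0.05 to 0.50 per patient-year.

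These sizes rest on an assumed constant rate and on groups that differ fully in follow-up. The actual imbalance depends on the number and status of the bridging subjects, which the documents do not give. The imbalance is therefore possible rather than shown, and its direction is open. This is an inexpensive improvement to reporting that should be made; it does not invalidate the safety analysis.

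**What to change.** In SAP 8.2, keep n (%) and make these changes.

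1. Add treatment-related AEs to the sentence on yearly rates, by subject status and overall, with 95% confidence intervals by the method of Ulm, already specified in SAP 5 for Poisson data. SOC-level rates are a useful option. PT-level rates can be left out because they will be sparse.
2. Define the denominator for all yearly rates in 8.2: time from the reported Revcovi start date in CLI-06814AA1-01 to the earliest of last dose + 30 days, study completion, study discontinuation or death. This matches the treatment-emergent window. The infection periods in 7.2.3 also stop at transplantation, so the two denominators differ and the SAP should say so.
3. Show total patient-years at risk in each column header.
4. Show the number of affected subjects beside each event rate, so that a rate driven by one subject is visible.
5. Footnote the percentage tables to say that percentages are not adjusted for exposure.

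The cost is SAP wording and a few table columns; the dates are already collected. The downside is slightly wider tables and imprecise rates in small groups, which the intervals will make plain.

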12.2.3 Serious Adverse Event

A *serious adverse event* (SAE) is an AE that in the view of either the Investigator or Sponsor, it results in any of the following outcomes:

- Death
- Is life-threatening (an event that in the view of either the Investigator or Sponsor, its occurrence places the subject at immediate risk of death; it does not include an event that had it occurred in a more severe form, might have caused death.)
- Requires in-subject hospitalization or prolongation of existing hospitalization
- Results in persistent or significant disability/incapacity or substantial disruption of the ability to conduct normal life functions
- Is a congenital anomaly or birth defect
- Is another important medical event that may not be immediately life-threatening or result in death or hospitalization but, based upon appropriate medical judgment, may jeopardize the subject or may require medical or surgical intervention to prevent one of the other outcomes listed above. Examples of such events are intensive treatment in an emergency room for allergic bronchospasm; blood dyscrasias or convulsions that do not result in hospitalization; or development of drug dependency or drug abuse.

The term "severe" is often used to describe the intensity (severity) of an event; the event itself may be of relatively minor medical significance (such as a severe headache). This is not the same as "serious", which is based on subject/event outcome or action criteria usually associated with events that pose a threat to a subject's life or functioning.

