4.2 As-Treated (AT) Population

The as-treated population, defined as all subjects who fulfill all eligibility criteria, had an informed consent form signed either by the patient or a legal guardian, are enrolled and receive at least one dose of Revcovi, will be the primary analysis set in all analyses. For the derivation of the AT population, the eligibility criteria will be used as collected in the eCRF.

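### SAP 8.2 counts adverse events with no seriousness flag as non-serious, and the SAP 4.2 safety set and the eCRF capture rule narrow the safety tables in ways their titles do not show

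*SAP*

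**What the plan says.** **Missing values.** SAP 8.2 on seriousness: "Adverse events missing the flag indicating serious will be excluded from the summary of serious adverse events"; these events are placed in the non-serious summary. On relationship: "Treatment-related adverse event summaries will include adverse events with missing relationship to study drug". On severity, a subject is counted at the worst grade available: "If all are of missing severity grade, then the AE term (SOC or PT) will be included in" a separate missing category. The section also reports total AE and SAE counts with yearly rates.

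**Safety set.** SAP 8: "The as-treated population will be used for all of the safety analyses". SAP 4.2 has that set "defined as all subjects who fulfill all eligibility criteria", with consent, enrolment and at least one dose, and adds: "For the derivation of the AT population, the eligibility criteria will be used as collected in the eCRF". Protocol 13.2.2 asks only for enrolment and one dose. SAP 8.1 declares no change from the protocol's safety analysis.

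**Capture.** SAP 8.2 opens by stating that "only infections, clinically meaningful laboratory abnormalities (except infections) and Revcovi related adverse events will be recorded in the eCRF". It then plans summaries of all treatment-emergent AEs, and of SAEs.

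**Causality.** Protocol 12.2.4 has five categories. *Possible*, *Probable* and *Definite* each need plausible timing and a recognised response pattern. *Unlikely* needs both to be absent and another ready cause. *Unrelated* needs a clearly different cause.

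**Laboratory status.** SAP 8.3 classes results with missing status as normal.

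**The concern.** The registry is a post-marketing commitment meant to add safety data (protocol 5.4), so its SAE table, yearly rate and AE tables will be taken at face value. Among the SAP 8.2 rules, only the seriousness rule assigns a missing value to the favourable category. SAP 13.5 leans the other way too: missing relationship is taken as related, and an AE with no onset date is generally taken as treatment-emergent.

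A safety set normally contains everyone exposed. Filtering it on eligibility can remove a treated subject's events from every safety table. A table described as covering all AEs also misleads if unrelated events outside two classes were never entered. Relatedness decides whether most events are recorded at all, so a hole in the causality scale bears on capture as well as on classification.

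**Working it through.** The plan has no sample size, test or safety figure to reproduce (protocol 13.1 and 13.2.1). The checks below use the text, with simple bounds where numbers help.

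**1. Missing seriousness.** Let S be the flagged SAEs and m the unflagged events that are truly serious. The table prints S, the truth is S + m, and the missed share is m/(S + m). I assume that the exclusion also applies to the yearly rate; its denominator does not depend on the flag, so the rate is low by the same share.

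| Missed share | Needs m of at least | Unflagged serious per flagged SAE |
|---|---|---|
| 5% | S/19 | 1 per 19 |
| 10% | S/9 | 1 per 9 |
| 20% | S/4 | 1 per 4 |

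The missed share is zero if every unflagged event is non-serious. As an illustration with assumed inputs, take 100 AEs, 20% of flagged events serious, M unflagged and a fraction s of those serious. The printed count is 0.2 × (100 − M), and M × s are missed.

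| M | s = 20% | s = 50% |
|---|---|---|
| 2 | 0.4/20.0 = 2.0% | 1.0/20.6 = 4.9% |
| 5 | 1.0/20.0 = 5.0% | 2.5/21.5 = 11.6% |
| 10 | 2.0/20.0 = 10.0% | 5.0/23.0 = 21.7% |

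Protocol 12.2.3 lists six SAE criteria. Two have a separate output even when the flag is missing: deaths are listed (SAP 8.2) and hospitalizations are analysed (SAP 7.2.3). The other four do not, including "Is another important medical event that may not be immediately life-threatening or result in death or hospitalization". Such an event still appears in the all-event, severity and non-serious tables, but nothing there identifies it as serious.

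**2. Safety set.** Some passages tie entry to eligibility:
- Protocol 7.3 gives a subject number to patients who meet the criteria.
- Protocol 9.1 and 11.1 enrol those who meet the criteria.

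Others leave room for a dosed subject who fails:
- Protocol 10.2 numbers every consented subject and dates enrolment at consent.
- SAP 6.2 plans a listing of eligibility failures.

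The infant criterion also varies. The protocol synopsis and SAP 3.1 join newborn screening and definitive testing with and/or; protocol 7.1 and 9.2 use and. An infant diagnosed by definitive testing alone meets one version of that item but not the other, and the documents do not show which one the eCRF uses.

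Dropping one subject from N, with k affected and p = k/N, changes the percentage as follows:
- subject affected: (k − 1)/(N − 1) − k/N = −(1 − p)/(N − 1)
- subject not affected: k/(N − 1) − k/N = p/(N − 1)

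The registry N is not given. For assumed N of 20, 30 and 40 and p = 50%, the shift is 0.5/19, 0.5/29 and 0.5/39, that is 2.6, 1.7 and 1.3 percentage points in either direction. An event seen in one subject only (5.0%, 3.3% or 2.5%) falls to 0 if that subject is the one dropped. At N = 6, the size of the earlier study in protocol 5.3.2, 3/6 (50%) becomes 2/5 (40%) or 3/5 (60%). Event counts can only fall; percentages can move either way.

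**3. Capture.**
- Protocol 10.5.1 and 10.5.2 send examination findings and clinically meaningful vital-sign changes to the AE form if they meet the AE definition. Under protocol 12.2.1 that definition does not depend on relatedness.
- Protocol 13.2.3.5 summarises abnormal vital signs as AEs.
- Protocol 14.5 has investigators report all SAEs, while protocol 12.4 asks only for related ones.

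None of these fits the SAP 8.2 limit. Protocol 12.3 can be read either way, and the conflict does not rest on it.

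**4. Causality.** Cross timing (2) × known pattern (2) × other cause none/ready/clear (3) × no improvement/improvement/improvement with recurrence (3) = 36 profiles. A clear other cause covers 12 (*Unrelated*), *Unlikely* covers 3, and *Possible*, *Probable* and *Definite* together cover 5. That is 20, leaving 16 with no category. Six of the 16 have plausible timing, no known pattern and no clear other cause. Removing only the known-pattern condition from *Possible* places the 3 with a ready alternative cause; the 3 with no alternative cause still fit nothing, because *Possible* also requires a ready alternative.

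**The case against.** Seriousness is an item for every AE (protocol 10.5.5 and 12.3), entered in a system with edit checks and manual queries (protocol 14.7.1). Few flags may be missing at lock, and the convention is disclosed. That limits the size, but not the direction or the lack of any tabulated count of missing flags. A reader might infer that an unflagged serious event disappears from the safety summaries. SAP 8.2 does not support that: what is lost is its identification as serious, and the AE listings remain.

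On the safety set, enrolment in the protocol can be read as already implying eligibility, with SAP 4.2 only spelling it out. The criteria are four broad patient groups and one discretionary exclusion, so a dosed but ineligible subject should be uncommon. The SAP is also based on protocol Version 4.0 (SAP 1), while the protocol supplied is Version 5.0, which may explain differences. These points stand as limits on size. They do not explain why SAP 6.2 expects eligibility failures, or why the texts should stay unreconciled.

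On capture, the limit is stated openly at the start of SAP 8.2, and the word all is attached there to treatment-emergent AEs, not to SAEs. It would be wrong to infer concealment; the fault is in the labels and the conflict with the protocol.

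On causality, the gap comes from a literal reading. Protocol 12.2.4 opens with a broad question about any relation to the product, and protocol 12.2.2 foresees reactions not in the package insert. The count of profiles is not evidence that any event was misclassified. Changing the scale now, after the interim analysis (SAP 10), would also mix ratings made under two definitions. All of this stands, and is why that part is secondary.

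**Conclusion.** The seriousness rule and the narrowed safety set are wrong as written and should be corrected. The first can only lower the SAE count and rate. The second can only lower event counts, moves percentages either way, and departs from protocol 13.2.2 while SAP 8.1 reports no change. The mismatch between the capture rule and the table scope is also real.

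The size is unknown and may be small: the documents give no rate of missing flags, SAE count, registry N or number of ineligible treated subjects, and every numerical example above rests on assumed values or on the earlier study. No size can be put on the capture or causality points. A reader might infer that serious events have been missed or that exposed subjects have already been lost from the tables. The documents show only that the rules allow it. Nothing here overturns a test, since the study has none. The laboratory-status rule affects listing flags only and is minor.

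**What to change.** 1. **Seriousness (SAP 8.2).** Query missing flags before database lock. Show any that remain in a missing-seriousness row, and add a sensitivity SAE count that treats them as serious. Cost: SAP wording and one small table.
2. **Safety set (SAP 4.2 and 8).** Use all enrolled subjects with at least one dose, keep the SAP 6.2 listing of eligibility failures, and align the SAP with the current protocol version. Reconcile the infant criterion between the protocol synopsis and SAP 3.1 on one side and protocol 7.1 and 9.2 on the other. Cost: SAP wording and one protocol reconciliation.
3. **Capture.** Reconcile SAP 8.2 with protocol 10.5.1, 10.5.2, 12.2.1 and 13.2.3.5, and protocol 14.5 with 12.4. Unless all AEs and SAEs are collected, title the AE and SAE tables by the capture rule. Cost: text and titles; no retrospective collection.
4. **Causality (secondary).** The sponsor should reconcile the protocol 12.2.4 definitions so that every plausibly timed event has a category, and state which definition applied to ratings already made. Cost: a protocol amendment with IRB approval (protocol 14.1.1), so this is separate from the inexpensive changes above.
5. **Laboratory listings (SAP 8.3).** Print that status is missing instead of normal. Cost: one listing change.
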